**Multicenter double-blind placebo-controlled randomized
parallel-group clinical study of efficacy and safety of Divaza
for adjustment of oxidative disorders in patients with
cerebral atherosclerosis**

Phase IV

Sponsor	OOO «NPF «MATERIA MEDICA HOLDING»
Protocol number	MMH-DV-010
Version date:	December 05, 2017

ClinicalTrials.gov Id: NCT03485495

Protocol Summary

This document represents the protocol summary for the study on human subjects. The study will be carried out in accordance with ICH GCP, National Standard of the Russian Federation GOST 52379-2005 "Good Clinical Practice", Helsinki Declaration of World Medical Association, relevant requirements of the regulatory authorities as well as the study procedures.

Title of Study

Multicenter double-blind placebo-controlled randomized parallel-group clinical study of efficacy and safety of Divaza for adjustment of oxidative disorders in patients with cerebral atherosclerosis

Phase: IV

Sponsor: OOO "NPF "MATERIA MEDICA HOLDING", Moscow, Russia

Protocol No. MMH-DV-010

Objective of the study

- To obtain additional data on efficacy and safety of Divaza for adjustment of oxidative disorders in patients with cerebral atherosclerosis.

Endpoints

Primary endpoint

- Change in mean value of lipoprotein resistance to LP after 12-week therapy vs. baseline.

Secondary endpoint

- Proportion of patients with improved cognitive function (MoCA score + 1 or more) after 12-week therapy versus baseline.

Exploratory endpoints

- Change in mean level of preformed LP products, predominantly lipid hydroperoxides after 12-week therapy versus baseline.
- Change in mean value of lipoprotein ability for oxidation after 12-week therapy versus baseline.
- Change in mean value of NO product serum concentration after 12-week therapy versus baseline.
- Change in mean value of platelet aggregation after 12-week therapy versus baseline.
- Change in mean IMCT value after 12-week therapy versus baseline.

Safety assessment

- Occurrence and nature of adverse events during the therapy, their intensity (severity), causal relationship to the study drug, and outcome.

Study design

Design – a multicenter randomized double-blind placebo-controlled parallel-group clinical trial.

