9. Desire of patient to complete the study ahead of schedule for any reason.
10. Participation in another clinical study.
11. Cases not specified by the protocol where the investigator decides that further participation may harm the patient.
12. Unblinding.

Number of subjects

It is planned to include 124 subjects which is expected to allow completion of all protocol procedures by at least 98 subjects (49 in each group).

Interim analysis

The protocol does not schedule any unblinded interim analyses, however, at the sponsor's decision a blinded interim analysis may be carried out to specify population parameters and potential further specification of sample size (increase only).

Treatment

Group 1

Name of the medicinal product: Divaza

Active ingredient: Affinity purified antibodies to brain-specific S-100 protein - 0.006 g*;
affinity purified antibodies to endothelial NO synthase - 0.006 g*

Excipients: Lactose monohydrate (lactose) - 0.267g; microcrystalline cellulose - 0.03 g;
magnesium stearate - 0.003 g

Method of administration: Tablet for oral use. Two tablets per intake 3 times a day (approximately at the same time), outside of meal (between meals or 15 minutes before eating or drinking). The tablets should be held in mouth until completely dissolved.

Dosage form: Tablets

Description: Scored and beveled flat cylindrical tablets, white to off-white

Storage conditions: Store at a temperature not exceeding 25° C.

Group 2

Name of the medicinal product: Placebo

Active ingredient: NA

Excipients: Lactose monohydrate (lactose) - 0.267 g, microcrystalline cellulose - 0.03 g;
magnesium stearate - 0.003 g

Method of administration: Tablet for oral use. Two tablets per intake 3 times a day (approximately at the same time), outside of meal (between meals or 15 minutes before eating or drinking). The tablets should be held in mouth until completely dissolved.

Dosage form: Tablets

Description: Scored and beveled flat cylindrical tablets, white to off-white

Storage conditions: Store at a temperature not exceeding 25° C.

Prohibited concomitant therapy

One month prior to enrollment and during the study (beginning from signing informed consent form and initiation of screening) it is prohibited to administer any therapy affecting neurological and oxidative status of the patient:

[figure not shown]
1. Products manufactured by OOO "NPF "Materia Medica Holding": Tenoten, Kolofort, Brizantin, Proproten, Afalaza, Impaza.

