- levels of preformed LP products, predominantly lipid hydroperoxides		+			+
- low and very low-density lipoprotein resistance to LP		+			+
- lipoprotein ability for oxidation		+			+
- serum levels of NO products		+			+
- platelet aggregation with bandage sign ⁶		+			+
Duplex MAH scanning ⁷		+			+
Pregnancy test ⁸	+				
End of patient participation in the study	+	+	+	+	+

Statistical Analyses

Samples

Total set includes all the patients who have signed ICF. This sample will consider all adverse events throughout the study, including those occurred prior to the study therapy.

The sample including all patients who received at least one dose of the study drug to be used for ***analysis of the study treatment safety and tolerability (Safety population)***, as all adverse events identified after the study drug administration will be recorded.

Full Analysis Set This sample will consist of all enrolled patients, except for those who met at least one of the following criteria:

- 1) noncompliance with inclusion/exclusion criteria;
- 2) patient failing to take any dose of the study drug;
- 3) lack of any data on the patient after the study drug administration.

This was the best set for the Intention-to-treat method, so it will be used in the ***Intention-to-treat efficacy analysis of the study therapy***.

Per Protocol set. This sample includes all patients who completed the therapy as per the study protocol, without any missing visits or major protocol deviations. This set will be used in the ***Per Protocol efficacy analysis of the test therapy***.

⁵ If applicable.

⁶ Will be performed for the patients in FSBRI Research Center of Neurology only.

⁷ Will be performed for the patients in FSBRI Research Center of Neurology only.

⁸ If applicable.

Per Protocol set will not include the subjects whose data are fully or partially invalid for analysis due to a protocol deviation.

Protocol deviations resulting in full or partial data invalidity.

1. Violation of visit schedule.
2. Inappropriate supply of the study drug.
3. Prescription of prohibited therapy.
4. $\geq 25\%$ increase or reduction in the amount of the study therapy administered.
5. Inability to assess the subject's compliance using the formula (e.g. loss of pack with the product).
6. Major discrepancies between source documents and CRF detected during monitoring or another authorized check.
7. Violation of the procedure for obtaining Informed consent.

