$z_{\alpha/2}$ – tabular value of two-sided z-criterion for α

z_β – tabular value of one-sided z-criterion for β ;

- Interval values:

$$n_1 = kn_2$$

$$n_2 = \frac{\left(\frac{z_\alpha}{2} + z_\beta\right)^2 \sigma^2 \left(1 + \frac{1}{k}\right)}{\epsilon^2}$$

where n_1, n_2 are sample sizes for Divaza and Placebo groups, respectively

$\epsilon = \Delta\mu_1 - \Delta\mu_2$ – expected difference between mean reductions of value between Divaza and Placebo groups

k – ratio of sample sizes (in this study $k=1$)

σ – standard deviation of reduction

$z_{\alpha/2}$ – tabular value of two-sided z-criterion for α

z_{β} – tabular value of one-sided z-criterion for β ;

- 1.8 the largest of the samples meeting the primary endpoint will be used for terminal PP sample size

$$N_{PP} = \max(n_1, n_2, \dots, n_i);$$

- 1.9 final sample size will be determined using the formula:

$$N_T = N_{PP} / (1 - C_w),$$

where N_T – final sample size;

N_{PP} – result of calculation in cl. 1.7 – cl. 1.8, i.e. the scheduled number of the patients completing the study per protocol

C_w – withdrawal coefficient.

2. Assumptions on expected clinical study effects.

Primary endpoint: difference in changes in activity of endogenous antioxidant protection between Divaza and Placebo groups will be no less than $\epsilon=20.36$ s at standard deviation of $\sigma=32.1$.

Secondary endpoint: Proportion of patients with reduced total MoCA score ≥ 1 in Divaza group will be no less than 82%, while in Placebo group the relevant value will be no more than 50%.

3. Total type I error is divided equally between the primary and secondary criteria.

To evaluate superiority of Divaza over Placebo, group size will be (49, 42) patients for each group, respectively, for the primary and secondary criteria.

Given potential withdrawal of at least 20% subjects ($R_w=0.2$) during the study for various reasons, at least 124 patients will be required to sign informed consent, with 62 patients per group.

Statistical criteria

All statistical calculations will be made using two groups of statistical criteria:

- parametric - to evaluate continuous and interval random values;
- nonparametric – to obtain:
 - evaluations of equality/inequality in the proportion of the patients upon their comparison for various visits,
 - analysis of frequencies of the features compared,and

- evaluation of continuous and interval random values in case of non-compliance with normal random distribution.

Parametric criteria

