The application of parametric criteria will be accompanied by a check of models for applicability (e.g. Kolmogorov-Smirnov test, Shapiro-Wilk test).

The following parameters and approaches are to be used:

1. To evaluate the differences in continuous variables obtained in one group at two different visits – Student’s test for paired samples.
2. To evaluate time changes in parameters compared - analysis of variance (ANOVA) or modified repeated measures covariance (ANCOVA).
3. In case of multiple comparisons of the groups various adjustments for multiplicity will be used (Dunnett, Tukey, Scheffe, Holm adapted test), etc.
4. Generalized Linear Models and/or Mixed Linear Models will be used in case of abnormal data distribution.
5. Selection of the type of distribution, specification of factor and covariance structures of the model will be made using fit-statistics such as AIC (Akaike information criterion).

The following SAS software programs are supposed to be applied to the above listed tests and techniques:

- UNIVARIATE: normality verification of the distributions under comparison;
- CORR, MEANS - calculation of descriptive statistics
- TTEST – Student’s test with all modifications;
- GLM – generalized linear models for analysis of time changes (ANOVA, ANCOVA);
- GENMOD – generalized linear models.
- MIXED – mixed linear models.

Non-parametric criteria

Below are potential types of comparisons with relevant criteria:

1. To evaluate time changes in the parameters compared – Friedman test, nonparametric analogue of repeated measures analysis of variance.
2. For frequency analysis of contingency tables 2×2 – χ^2 (if the frequency under comparison > 5) or exact Fisher’s test (if one of the frequencies under comparison < 5).
3. Cochran-Mantel-Haenszel test (modified χ^2 test for multiple comparisons) – to perform frequency analysis based on independent strata.
4. For frequency analysis of data on presence/absence of an event or outcome during repeated measurements (contingency tables with dependent strata) – survival analysis.

To perform the above-mentioned nonparametric statistical analysis the following SAS procedures are to be used:

- FREQ – Friedman test, χ^2 test and/or exact Fisher's test; Cochran-Mantel-Haenszel test.
- LIFETEST, PHREG – survival analysis.
- NPAR1WAY - Mann-Whitney U-test.

Safety parameters

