Adverse events recorded during the study will be grouped into frequency tables by severity, seriousness and relationship with the study drug.

Data presentation

Descriptive statistics will be provided for each study continuous / interval variable. Numerical data will be presented by mean, standard deviation, min and max values. Comparisons suggesting statistical conclusion will have the relevant confidence intervals. Outliers will be analyzed individually. The data will be grouped by visits. The categorical variables will be presented as frequency tables by visits.

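### The equal alpha split is valid and the planned power is met, but adding a Holm step between the two endpoints would raise primary power at the same sample size

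*Combined protocol and SAP*

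**What the plan says.** Under 'Evaluation of sample size', item 3 reads "Total type I error is divided equally between the primary and secondary criteria". The same section sets two-sided tests, an overall type I error below 5% and 80% power. It gives group sizes of 49 for the primary endpoint and 42 for the secondary, and 124 patients signing consent (62 per group) after a 20% withdrawal allowance. Item 1.9 sizes the trial on "the scheduled number of the patients completing the study per protocol".

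The only other multiplicity text is item 3 of 'Parametric criteria': "In case of multiple comparisons of the groups various adjustments for multiplicity will be used". A Holm-type test is one entry in the open list that follows.

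'Samples' plans an intention-to-treat efficacy analysis on the Full Analysis Set ("This was the best set for the Intention-to-treat method") and a second efficacy analysis on the Per Protocol set. It does not say which one decides.

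'Non-parametric criteria', item 2, analyses 2×2 tables by chi-square, with Fisher's exact test "if one of the frequencies under comparison < 5". 'Data presentation' adds: "Comparisons suggesting statistical conclusion will have the relevant confidence intervals".

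The text opens with "This document represents the protocol summary for the study on human subjects", so a fuller protocol may say more.

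**The concern.** An equal split with no further rule leaves alpha unused. Once one endpoint is rejected at 0.025, Holm allows the other to be tested at 0.05 with familywise error still at 5%, provided each test holds its own level. The summary contains no such step. Its one mention of Holm concerns comparisons between groups, and this trial has only two. Read naturally, the plan fixes each endpoint at 0.025, so a primary p between 0.025 and 0.05 is lost however strong the MoCA result is.

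A second gap bears on any such rule. With two efficacy sets and no ranking, the choice of which p-values enter the decision stays open after unblinding.

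**Working it through.** **Inputs.** From 'Evaluation of sample size': primary difference 20.36 s with SD 32.1 (d = 20.36/32.1 = 0.634); MoCA 82% v 50%; 1:1 allocation; 49 per arm completing and 62 per arm consenting. The 82% and 50% are read as improvement rates, as in the endpoint definition and the hypotheses, although the effect assumption speaks of a reduced score. Assumed, because the documents do not settle it: a t-test for the primary, chi-square for MoCA unless stated, and independent endpoints in the base case.

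**The plan's own figures.**
- Primary, normal formula at 0.025: n = 2 × (32.1 × (2.241 + 0.842)/20.36)² = 47.3, so 48. By noncentral t, power is 79.5% at 48 and 80.4% at 49, so the t version gives the stated 49.
- Secondary: the pooled formula at 0.025 gives 41, against the stated 42. The printed unpooled formula gives 37.
- Two-sided 0.05 would give only 40 for the primary, so the plan did size at 0.025.
- Withdrawal: 49/(1 − 0.2) = 61.25, so 62 per arm and 124 in total.
- Familywise error of the split: at most 0.025 + 0.025 = 0.05, or 1 − 0.975² = 0.0494 if independent.

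**Power at each level** (noncentral t; exact binomial enumeration of the pooled chi-square and Fisher tests).

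| n per arm | Primary 0.025 / 0.05 | MoCA chi-square 0.025 / 0.05 | MoCA Fisher 0.025 / 0.05 |
|---|---|---|---|
| 49 | 0.8042 / 0.8745 | 0.884 / 0.928 | 0.838 / 0.896 |
| 62 | 0.8950 / 0.9387 | 0.949 / 0.972 | 0.927 / 0.958 |

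**Primary power under Holm** = P(0.025) + [P(0.05) − P(0.025)] × MoCA power at 0.025.
- 49 per arm: 0.8042 + 0.0703 × 0.884 = 0.866, a gain of 6.2 points.
- 62 per arm: 0.8950 + 0.0437 × 0.949 = 0.936, a gain of 4.1 points.

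**Sensitivity of the gain.**
- Divaza MoCA rate 70%: MoCA power at 0.025 is 0.422 (49) and 0.510 (62), so the gain is 3.0 and 2.2 points.
- Divaza MoCA rate 60%: MoCA power is 0.101 and 0.128, so the gain is 0.7 and 0.6 points.
- Assumed patient-level correlation 0.8 (simulation): 5.4 and 3.7 points.
- Both effects at 75% of plan, 62 per arm: 64.8% to 71.8%.

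**False-positive rate of one endpoint when the other effect is real.**
- Primary null, MoCA as planned: 0.025 + 0.025 × 0.884 = 4.7% (49); 0.025 + 0.025 × 0.949 = 4.9% (62).
- MoCA null at a common 50%, chi-square: 0.0217 + (0.0544 − 0.0217) × 0.804 = 4.8% (49); 0.0244 + (0.0589 − 0.0244) × 0.895 = 5.5% (62). The excess over 5% comes from chi-square exceeding its own nominal level, not from Holm. The plan's cell-count rule would normally select chi-square here: at 82% improved, about 0.18 × 49 = 9 to 0.18 × 62 = 11 Divaza patients would be non-improvers.

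**MoCA power, Fisher with Holm against chi-square with the split.**
- Primary effect as planned: 88.5% against 88.4% (49); 95.5% against 94.9% (62).
- Primary null: 0.838 + (0.896 − 0.838) × 0.025 = 83.9% against 88.4% (49); 92.8% against 94.9% (62).
- Both effects at 75% of plan, 49 per arm: 57.3% against 59.9%.

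**The case against.** The strongest reply is that nothing is broken. The split is valid, the trial is sized for it and planned power is reached, so preferring Holm is a design choice. The plan also gives a reason to keep the split: it promises confidence intervals, and simple 97.5% intervals for the primary always agree with a 0.025 decision, whereas under Holm they need not. All of this stands, and it is why the point is only an improvement.

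It can also be said that item 3 is a sizing assumption and not a decision rule, and that Holm starts from the same 0.025. That is fair. A reader might infer that the plan rules Holm out, but the text is silent, and a fuller protocol may settle the matter. What the summary does not do is state the step.

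Three stronger readings should be resisted:
- That the split inflates type I error or underpowers the trial. The figures above show neither.
- That moving the decision to the Full Analysis Set produces the gain. The gain comes from Holm alone. If effects are diluted in that set, power there can fall below the planning figure: 71.8% with Holm at 75% of plan, even at 62 per arm.
- That Fisher's test must come with Holm. It buys strict 5% control, but lowers MoCA power when the primary effect is absent or smaller than planned.

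Finally, 62 per arm is optimistic because 124 counts patients signing consent; 49 is the completer case. And the plan names no single test for the primary, so one p-value per endpoint must be defined before any decision rule, the split included, can be applied.

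**Conclusion.** This is a cheap improvement and not an error. With the same tests, Holm rejects everything the split rejects and sometimes more, with no extra patients and the same 5% familywise limit if each test is valid. Under the plan's effects and the assumed independence, the primary gains about 6 points of power at 49 per arm and about 4 at the 62-per-arm ceiling. The gain is never negative within a given analysis set and choice of tests, but it depends on MoCA succeeding and nearly disappears if that effect is small. The unranked efficacy sets are a separate gap in prespecification: closing it removes a choice after unblinding and adds no power. Both conclusions rest on the protocol summary alone.

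**What to change.** Before unblinding, keep the sample-size calculation at 0.025 and add to 'Statistical criteria':

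> Familywise two-sided type I error of 5% across the primary and secondary endpoints is controlled by the Holm procedure: the smaller p-value is tested at 0.025 and, if significant, the other at 0.05.

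State also which efficacy set supplies the two p-values, with the other set supportive, and that each endpoint contributes one p-value from one prespecified test. If a fuller protocol already names the deciding set, keep it and add only the Holm sentence.

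Fisher's exact test for MoCA, whatever the cell counts, is optional. Choose it if strict 5% control is wanted, and record the MoCA power cost shown above. If nominal control is acceptable, chi-square may stay.

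The change costs a few sentences and no patients. Two consequences should be stated with it: an endpoint accepted at p between 0.025 and 0.05 can have a simple 97.5% interval that includes no effect, and one endpoint's false-positive rate approaches 5% (about 5.5% for MoCA by chi-square at 62 per arm and a common rate of 50%) when the other has a true effect.

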8. Non-compliance with the clinical study protocol procedures.
9. Inability to collect all subject's data used for evaluation of the study endpoints (e.g. lack of entries in source documents required for verification of inclusion/exclusion criteria, safety and efficacy criteria).
10. Other protocol deviations resulting in full or partial data invalidity.

Data treatment and all statistical calculations under the protocol will be made using SAS-9.4 statistical software.⁹

Evaluation of sample size

The sample size was assessed in accordance with the following rules and assumptions:

1. Statistical assumptions
 - 1.1 the power of statistical tests ' $P = (1 - \beta)$ ' is 80% (the probability of correct rejection of the null hypothesis is 0.8)
 - 1.2 the probability of type I error ' α ' is less than 5% (the probability of false acceptance of the alternative hypothesis is less than 0.05);
 - 1.3 statistical criteria will be two-sided;
 - 1.4 calculation of sample size will be based on the assumptions on the expected effect declared in the primary and secondary endpoints of the protocol;
 - 1.5 ratio between Divaza and Placebo sample sizes is 1:1 (1 Divaza subject per 1 Placebo subject);
 - 1.6 statistical hypotheses will be as follows:
 - Binary values:

⁹ Holder of license: OOO "NPF "MATERIA MEDICA HOLDING", No. 70100045.

null and alternative hypotheses on superiority of the study product under the dosing scheme used:

$$\mathbf{H}_0: p_1=p_2$$

$$\mathbf{H}_a: p_1 \neq p_2$$

p_1 – proportion of patients in Divaza group with ≥ 1 improvement

p_2 – proportion of patients in Placebo group with ≥ 1 improvement

- Interval values

null and alternative hypotheses on superiority of the study product under the dosing scheme used:

$$\mathbf{H}_0: \Delta\mu_1=\Delta\mu_2$$

$$\mathbf{H}_a: \Delta\mu_1 \neq \Delta\mu_2$$

where $\Delta\mu_1$ – mean reduction (initial – final score) in Divaza group

$\Delta\mu_2$ – mean reduction (initial – final score) in Placebo group;

1.7 calculation of sample size for statistical criteria will be made using the following formulas:

- Binary values:

$$n_1 = kn_2$$

$$n_2 = \frac{\left(\frac{z_\alpha}{2} + z_\beta\right)^2}{\epsilon^2} \left[\frac{p_1(1-p_1)}{k} + p_2(1-p_2) \right]$$

where n_1, n_2 are sample sizes for Divaza and Placebo groups

$\epsilon = p_1 - p_2$ – expected difference between proportions of subjects with improvement in Divaza and Placebo groups

k – ratio of sample sizes (in this study equal to 1)

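### A normality check with two conflicting outcomes decides the primary method, so the planned difference in mean change can give way to another comparison after the data are seen

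*Combined protocol and SAP*

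**What the plan says.** **Target.** The Endpoints section defines the primary endpoint as the change in a mean value at 12 weeks. Item 1.6 under Evaluation of sample size states the interval-scale hypothesis as equality of the two arms' mean reductions. The same section assumes a difference of 20.36 s with SD 32.1. It also says "statistical criteria will be two-sided" and "Total type I error is divided equally between the primary and secondary criteria".

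**Method.** No single between-arm test or model is named for the primary endpoint. The choice depends on normality:

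- Statistical criteria assigns to the nonparametric group "evaluation of continuous and interval random values in case of non-compliance with normal random distribution".
- Parametric criteria, item 4, says of the same situation: "Generalized Linear Models and/or Mixed Linear Models will be used in case of abnormal data distribution".
- Item 5 continues: "Selection of the type of distribution, specification of factor and covariance structures of the model will be made using fit-statistics such as AIC".
- Kolmogorov-Smirnov and Shapiro-Wilk are given as examples of the check, without a significance level. The list of SAS procedures describes it as "UNIVARIATE: normality verification of the distributions under comparison".
- Mann-Whitney, the rank test for two groups, appears only in the SAS procedure list.

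**The concern.** The two instructions share a trigger, lead to different method families, and are not ranked. Several further choices follow from them.

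- **The second route is partly not a remedy.** A generalized linear model can accommodate a non-normal response. A linear mixed model as fitted by PROC MIXED assumes normal residuals and random effects, so moving to it because normality failed does not address the failure.
- **The object of the check is not stated.** The text would fit raw visit values or changes, and it also speaks of checking models. Residuals are never mentioned.
- **The final model is chosen on outcome data.** Item 5 leaves distribution and factors to AIC, and no step in the document fixes the choice before unblinding.

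What is at stake is mainly the question being answered. Mann-Whitney does not test equality of means. A generalized linear model with a non-identity link compares the arms on another scale. Neither is the 20.36 s difference in mean change for which the trial is sized.

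**Working it through.** **1. Reproduce the plan's figure.** Inputs from Evaluation of sample size: ε = 20.36 s, σ = 32.1, power 80%, k = 1, and total α 0.05 split equally, so 0.05/2 = 0.025 for the primary.

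n = 2σ²(z₀.₉₈₇₅ + z₀.₈)²/ε² = 2 × 1030.41 × (2.2414 + 0.8416)²/414.53 = 47.25, so 48 per group. The noncentral t calculation gives 49 (power 80.4%), which is the stated figure. At α = 0.05 the two methods give 40 and 41. The stated 49 therefore rests on a two-sample comparison of mean changes at 0.025. With 20% withdrawal, 49/0.8 = 61.25, so 62 per group and 124 in total, as stated.

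**2. Choice between t-test and Mann-Whitney, arms of the same shape.** Simulation with 49 per arm, two-sided 0.025 and 10,000 trials per row. Shapiro-Wilk is applied in each arm at 0.05. The shapes and that 0.05 are assumptions, because the plan gives neither. Monte Carlo standard error near 2.5% is √(0.025 × 0.975/10,000) ≈ 0.16 points. All columns are percentages under no effect, except the last two, which give power at 20.36/32.1 = 0.634 SD.

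| Shape of change | Flagged non-normal | t-test error | Strict switch error | Smaller p if flagged | t-test power | Mann-Whitney power |
|---|---|---|---|---|---|---|
| Normal | 9.6 | 2.5 | 2.5 | 2.6 | 80.2 | 78.1 |
| t, 5 df | 59.1 | 2.5 | 2.7 | 3.2 | 80.5 | 87.2 |
| Lognormal 0.5 | 99.4 | 2.2 | 2.3 | 3.2 | 80.7 | 93.3 |
| Exponential | 100 | 2.3 | 2.5 | 3.5 | 79.7 | 97.0 |
| Lognormal 1 | 100 | 1.7 | 2.5 | 3.5 | 83.2 | 99.95 |

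The normal row behaves as expected: two checks at 0.05 flag 1 − 0.95² = 9.75% of trials. A strict switch is near nominal. Leaving both tests open once data are flagged raises error to 2.6-3.5%.

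**3. Adding ANCOVA.** Lognormal visit values (sigma 0.2-0.3, correlation between visits 0.5-0.8), 49 per arm, no effect, 6,000 trials per setting:

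- t-test alone: 2.4-2.6%.
- Smaller p of t-test and Mann-Whitney, only when changes fail Shapiro-Wilk: 2.7-2.9%.
- Smaller p of t-test and ANCOVA, with no normality rule involved: 3.3-3.6%.
- Smallest p of all three: 3.6-4.2%.

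A run with 2,000 trials per setting gave 3.4-4.2% for all three. A coarser run with 1,500 gave 3.3-5.0%, and 2.2-3.5% for a strict switch. Measured from 2.5%, the t-test/ANCOVA choice accounts for roughly 0.8-1.1 of the 1.1-1.7 points of inflation.

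**4. What is checked matters.** In the same lognormal settings (2,000 trials each), Shapiro-Wilk rejects in 69-95% of trials if raw values are checked and in 18-34% if changes are checked. The unstated object of the check can thus decide which route is taken.

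**5. Equal means, different shapes.** Exponential against normal arms, equal means, 8,000 trials: the t-test rejects in 2.9% and Mann-Whitney in 6.1%. Every trial was flagged, so a strict switch also gives 6.1%. A repeat gave 2.5% and 5.9%.

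**The case against.** The strongest reply is that the numerical harm is small. A mechanical switch holds its level when the arms have the same shape, and the larger part of the inflation comes from the open t-test/ANCOVA choice, which has nothing to do with normality. This stands. It is also true that under a pure shift in skewed data the rank test is the more powerful one (93.3% against 80.7% in the milder lognormal row). That would support naming a rank test in advance, with a hypothesis to match. It does not support letting the data choose. The 6% result needs arms of different shape, which is an assumption.

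Four stronger readings are tempting, and the documents do not support them:

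- **That raw values are tested for normality.** Item 1.6 compares reductions, so the distributions under comparison may well be changes. The supportable criticism is that the text does not say.
- **That AIC selection itself inflates error badly.** AIC choice of main-effect covariates gave 2.7% against 2.5% in 3,000 trials. A figure of about 14% arises only if AIC may add treatment interactions and any significant one counts as success, which no section permits.
- **That the plan misuses REML-based AIC or fits positive-only distributions to changes.** It mentions neither REML nor any such distribution. These are possible misapplications, not stated rules.
- **That a named primary test is being replaced.** None is named. The mean comparison is implied by the endpoint, hypothesis and sample size.

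The document also calls itself a protocol summary and introduces the nonparametric list as potential comparisons. That may explain the brevity, but it does not reconcile two instructions for the same condition.

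**Conclusion.** The point holds and should be corrected. The rules for non-normal data conflict, half of one route is no remedy, the object and level of the check are unstated, and the final model is left to AIC on trial data. The main consequence is that the primary result may not answer the stated hypothesis about mean change. Inflation is secondary: near 2.5% for a strict switch with same-shaped arms, about 3.4-4.2% if t-test, ANCOVA and Mann-Whitney all stay open, and about 6% for Mann-Whitney in the one equal-means, different-shapes case tried. All of these rest on assumed distributions and a 0.05 check level. The sample size is not in question. Nothing in the documents suggests an intention to choose the most favourable result; the weakness is that the text would not prevent it.

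**What to change.** For the primary endpoint, name one analysis that applies whatever any normality test shows: the between-arm difference in mean 12-week change, in seconds, from an ANCOVA with the baseline value as covariate and HC3 robust standard errors, at two-sided 0.025. This also closes the t-test/ANCOVA choice. State that the normality check and Parametric criteria items 4 and 5 do not apply to the primary endpoint. Keep one rank analysis of change as a sensitivity analysis, and confine AIC-based selection to exploratory models. Leave the secondary endpoint out of this change: it is binary, the normality check does not bear on it, and a generalized linear model is a legitimate tool there.

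The cost is SAP wording. The sample size stays at 49 per group, 62 after withdrawal and 124 in total, since adjusting for baseline does not enlarge the residual variance on which 49 is based. The simple mean comparison held 1.7-2.5% error and about 80-83% power across the five same-shape cases, and a fixed ANCOVA gave 2.5% in 3,000 null trials. The HC3 version was not simulated separately.
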